**Table 12–3: Required investigations and follow up for PDILI**

Laboratory value			Immediate		Follow up	
ALT or AST	Total bilirubin	Symptoms a of hepatitis of hypersensitivity	Consultation requirements	Actions	Testing	Evaluation
≥3xULN	≥2xULN b	NA	Hepatology consult c Medical Monitor must be notified within 24 hours (eg, by laboratory alert) and subject discussed with Medical Monitor ASAP.	Immediate, permanent IMP discontinuation.	Essential: Must have repeat liver chemistry values and additional testing completed ASAP (see Section 12.5.1.4 ); recommended to occur at the site with HCP.	Monitoring of liver chemistry values at least twice per week until values normalize, stabilize, or return to within baseline values. d
≥3xULN	NA	Yes				
≥5xULN	NA	NA	Need for hepatology consult to be discussed. (required if ALT or AST ≥8xULN) Medical Monitor must be notified within 24 hours (eg, by laboratory alert) and subject discussed with Medical Monitor ASAP.	Immediate, permanent IMP discontinuation		

**Table 12–3: Required investigations and follow up for PDILI**

Laboratory value			Immediate		Follow up	
ALT or AST	Total bilirubin	Symptoms a of hepatitis of hypersensitivity	Consultation requirements	Actions	Testing	Evaluation
≥3xULN (and ≥2x baseline) and <5xULN (and ≥2x baseline)	<2xULN	No	
Discussion with Medical Monitor required.
 
Consider need for hepatology consult if there is no evidence of resolution (see Follow up requirements).c
	
Further investigation – immediate IMP discontinuation not required (see Section 12.5.1.2).
 
IMP discontinuation required if any of the following occur:
 
 
• Subject cannot comply with monitoring schedule.
 
• Liver chemistry values continue to increase
 
• Liver chemistry values remain ≥3xULN (and ≥2x baseline) after 2 weeks of monitoring without evidence of resolution
 
	
Essential: Every attempt must be made to have repeat liver chemistry values and additional testing completed within 48 hours at the site with HCP (see Section 12.5.1.4).
	
Monitoring of liver chemistry values at least twice per week for 2 weeks.d
 
 
• Immediate IMP discontinuation required if liver chemistry values continue to increase.
 
 
After 2 weeks of monitoring liver chemistry values:
 
 
• Discontinue IMP if levels remain ≥3xULN (and ≥2x baseline) without evidence of resolutiond
 
 
Continue to monitor until values normalize, stabilize, or return to within baseline values.d

**Table 12–3: Required investigations and follow up for PDILI**

Laboratory value		Symptoms a of hepatitis of hypersensitivity	Immediate		Follow up	
ALT or AST	Total bilirubin		Consultation requirements	Actions	Testing	Evaluation

ALT=alanine aminotransferase; ASAP=as soon as possible; AST=aspartate aminotransferase; HCP=healthcare practitioner; IMP=investigational medicinal product; NA=not applicable; PDILI=potential drug-induced liver injury; ULN=upper limit of normal

a Hepatitis symptoms include fatigue, nausea, vomiting, and right upper quadrant pain or tenderness; hypersensitivity symptoms include eosinophilia (>5%), rash, and fever (without clear alternative cause).

b If the subject also has  $\geq 2 \times$ ULN ALP, the possibility of an indication of biliary obstruction should be discussed with the Medical Monitor.

c Details provided in [Section 12.5.1.1](#). The local hepatologist is the expert usually consulted by the treating physician for assessment and management of potential hepatic disease. This would usually be a hepatologist, but may be a gastroenterologist.

d Unless an alternative monitoring schedule is agreed by the investigator and UCB responsible physician. Determination of stabilization is at the discretion of the investigator in consultation with the hepatologist (as applicable) and UCB responsible physician, as needed.

This document cannot be used to support any marketing authorization application and any extensions of any marketing authorization

### **12.5.1.1 Consultation with Medical Monitor and local hepatologist**

Potential drug-induced liver injury events require notification of the Medical Monitor within 24 hours (eg, by laboratory alert), and the subject must be discussed with the Medical Monitor as soon as possible. If required, the subject must also be discussed with the local hepatologist. The local hepatologist is the expert usually consulted by the treating physician for assessment and management of potential hepatic disease. This would usually be a hepatologist, but may be a gastroenterologist. If determined necessary, this discussion should be followed by a full hepatology assessment (see [Section 12.5.1.4](#)) and SAE report (if applicable).

### **12.5.1.2 Immediate action: determination of IMP discontinuation**

All PDILI events require immediate action, testing, and monitoring.

The immediate action is dependent on the laboratory values and symptoms of hepatitis or hypersensitivity and ranges from continuation of IMP (followed by immediate investigation) to immediate and permanent discontinuation (see [Section 6.3.1](#) and [Table 12-3](#) for details).

When IMP is discontinued, all concomitant medications and herbal supplements that are not medically necessary should also be discontinued. The investigator should also consider dose reduction for medically necessary concomitant medication and consider changing any medically required concomitant medication known to be hepatotoxic to a suitable alternative.

### **12.5.1.3 IMP restart/rechallenge**

Rechallenge with a substance potentially causing drug-induced liver injury is dangerous, may be fatal, and must not occur.

### **12.5.1.4 Testing: identification/exclusion of alternative etiology**

The measurements and additional information required for the assessment of PDILI events when there is a reasonable possibility that they may have been caused by the IMP are included but not limited to those listed in [Table 12-4](#) (laboratory measurements) and [Table 12-5](#) (additional information). Results of the laboratory measurements and information collected are to be submitted to the sponsor on the corresponding CRF. If the medical history of the subject indicates a requirement for other assessments not included below, these additional assessments should be completed and submitted, as applicable.

All blood samples should be stored, if possible. If tests are done locally for more rapid results, a concurrent sample must also be sent to the central laboratory.

The following measurements are to be assessed:

**Table 12–4: PDILI laboratory measurements**

Virology-related	Hepatitis A IgM antibody
	HBsAg
	Hepatitis E IgM antibody
	HBcAb-IgM
	Hepatitis C RNA
	Cytomegalovirus IgM antibody
	Epstein-Barr viral capsid antigen IgM antibody (if unavailable, obtain heterophile antibody or monospot testing)
Immunology	Anti-nuclear antibody (qualitative and quantitative)
	Anti-smooth muscle antibody (qualitative and quantitative)
	Type 1 anti-liver kidney microsomal antibodies (qualitative and/or quantitative)
Hematology	Eosinophil count
Urinalysis	Toxicology screen a
Chemistry	Amylase
	If total bilirubin $\geq 1.5 \times \text{ULN}$ , obtain fractionated bilirubin to obtain % direct bilirubin
	Serum CPK and LDH to evaluate possible muscle injury causing transaminase elevation
Additional	Prothrombin time/INR b
	Serum pregnancy test
	PK sample

ALT=alanine aminotransferase; CPK=creatine phosphokinase; HBcAb-IgM=hepatitis B core antibody-IgM; HBsAg=hepatitis B surface antigen; IgM=immunoglobulin M; INR=international normalized ratio; LDH=lactate dehydrogenase; PDILI=potential drug-induced liver injury; PK=pharmacokinetic; RNA=ribonucleic acid; ULN=upper limit of normal

a For detecting substances such as amphetamines, benzodiazepines, opioids, marijuana, cocaine, phencyclidine, and tricyclic antidepressants. Additional tests may be performed based on the investigator's medical judgment and patient's history.

b Measured only for subjects with ALT  $> 8 \times \text{ULN}$ , elevations in total bilirubin, and symptoms of hepatitis or hypersensitivity. Hepatitis symptoms include fatigue, nausea, vomiting, and right upper quadrant pain or tenderness; hypersensitivity symptoms include eosinophilia ( $> 5\%$ ), rash, and fever (without clear alternative cause).

The following additional information is to be collected:

**Table 12–5: PDILI information to be collected**

New or updated information
Concomitant prescription and over-the-counter medications (eg, acetaminophen, herbal remedies, vitamins); dosages and dates should be included.

Pertinent medical history, including the following:
 
 
• History of liver disease (eg, autoimmune hepatitis, nonalcoholic steatohepatitis or other “fatty liver disease”)
 
• Adverse reactions to drugs
 
• Allergies
 
• Relevant family history or inheritable disorders (eg, Gilbert’s syndrome, alpha-1 antitrypsin deficiency)
 
• Recent travel
 
 
Progression of malignancy involving the liver (Note: Metastatic disease to the liver, by itself, should not be used as an explanation for significant AST and/or ALT elevations.)

The appearance or worsening of clinical symptoms of hepatitis or hypersensitivity (eg, fatigue, nausea, vomiting, right upper quadrant pain or tenderness, decreased appetite, abdominal pain, jaundice, fever, or rash)
Recent clinically significant hypotension or hypoxemia with compromised cardiopulmonary function
Alcohol and illicit drug use
Results of liver imaging or liver biopsy, if done
Results of any specialist or hepatology consult, if done
Any postmortem/pathology reports

ALT=alanine aminotransferase; AST=aspartate aminotransferase; PDILI=potential drug-induced liver injury

### **12.5.1.5 Follow-up evaluation**

Potential drug-induced liver injury events require follow-up monitoring as described in [Table 12–3](#). Monitoring should continue until liver chemistry values normalize, stabilize, or return to baseline. Determination of stabilization is at the discretion of the investigator in consultation with the hepatologist (as applicable) and UCB responsible physician, as needed.

## **12.6 Other safety measurements**

### **12.6.1 Assessment and management of TB and TB risk factors**

All subjects will be assessed for tuberculosis (TB) at Screening and at the timepoints specified in the Schedule of Assessments ([Table 5–1](#)) through physical examination for signs and symptoms of TB, chest x-ray ([Section 12.6.1.2](#)), laboratory testing ([Section 12.6.1.1](#)), and subject questionnaire ([Section 12.6.1.3](#)).

At Screening, all subjects will have an IGRA test (QuantiFERON TB GOLD is recommended), a chest x-ray (unless already performed within 3 months of Screening) and examination for signs

and symptoms of TB. In addition, each subject will complete a TB questionnaire with questions directed at symptoms of TB and potential exposure to TB.

#### Exclusion criteria at Screening

Subjects with known TB infection, at high risk of acquiring TB infection, or latent TB infection are excluded.

- a. Known TB infection whether present or past is defined as:
  - Active TB infection or clinical signs and symptoms suspicious for TB (pulmonary or extra-pulmonary)
  - History of active TB infection involving any organ system or findings in other organ systems consistent with TB infection, unless adequately treated and proven to be fully recovered upon consult with a TB specialist.
  - Any evidence by radiography or other imaging modalities consistent with previously active TB infection that is not reported in the subject's medical history
- b. High risk of acquiring TB infection is defined as:
  - Known exposure to another person with active TB infection within the 3 months prior to Screening
  - Time spent in a healthcare delivery setting or institution where individuals infected with TB are housed and where the risk of transmission of infection is high
- c. Latent TB infection is defined as:
  - The absence of signs, symptoms (ie, evidence of organ-specific involvement), or physical findings suggestive of TB infection with a positive IGRA test (or 2 indeterminate IGRA test results) and a chest x-ray (or other imaging) without evidence of TB infection. If the result of the IGRA test is indeterminate, the particular IGRA test previously performed may be repeated once; if positive or indeterminate on retest, the subject may not be randomized to study medication. The retest must be done during the protocol-defined Screening window (up to 4 weeks).

Note: If available, respiratory or other specimens must also be smear and culture negative for TB (Centers for Disease Control [CDC] diagnosis of LTB infection) <http://www.cdc.gov/TB/topic/testing/default.htm>)
- d. Current or history of nontuberculous mycobacterial (NTMB) infection despite prior or current therapy.

#### Signs and Symptoms

The Investigator should consider all potential sites of infection when assessing for TB during the physical examination, and other evaluations, and based on the subject's medical or social history.

The most common primary focus of TB is the lung. Other sites may include gastrointestinal system, bone/joints, lymph glands and meninges etc. However, in immune compromised patients and/or patients treated with TNF inhibitors, extra-pulmonary manifestations of TB is common compared to normal population.

Some common symptoms that the subject may present are dependent on the primary focus of infection and may include cough, blood in sputum, night sweats, lymphadenitis, joint pain/swelling, spinal deformity, headache/confusion, abdominal pain (mimicking inflammatory bowel disease), etc. Unusual presentations should always be considered.

LTBI is defined in the “Exclusion Criteria” above. If the result of the IGRA is indeterminate, the particular IGRA previously performed may be repeated once; if positive or indeterminate on retest, the subject may not be randomized to study medication. If LTBI or active TB is identified, subject must undergo appropriate study specified withdrawal procedures. The retest must be done during the protocol-defined Screening window (up to 4 weeks). Laboratory diagnosis should be undertaken via mycobacteria culture media (or if available by preferred nucleic acid amplification test such as the Xpert MTB RIF test) and result must be negative for TB inducing pathogens.

#### Test Conversion

Tuberculosis test conversion is defined as a positive IGRA result for the current test when previous IGRA test results were negative. All subjects with TB test conversion must immediately stop study drug administration. In case of a TB test conversion, the subject must be considered as having either a suspected new latent or an active TB infection and be promptly referred to an appropriate specialist (eg, pulmonologist, infectious disease specialist) for further evaluation. If test conversion indicates LTBI, active TB, or NTMB then, per UCB TB working instructions, TB test conversion (confirmed) should be classified adequately, either as due to LTBI, active TB infection, or NTMB, respectively. Additional assessments (eg, blood tests or IGRA, chest x-rays, or other imaging) should be performed where medically relevant and documented. Such conversions should be reported to the UCB Drug Safety function.

#### Latent TB

In case the evaluation by the appropriate specialist indicates a new LTBI during the study, a prophylactic TB treatment should be initiated and the subject must be withdrawn from the study.

Every related action should be discussed in advance with the Medical Monitor.

Once withdrawn from study treatment, subjects should return for the Week 36/EWD Visit, complete all Early Withdrawal Visit assessments, and complete a SFU Visit (20 weeks after the last dose of study medication).

#### Active TB or nontuberculosis mycobacterium infection

Subjects who develop active TB or NTMB infection during the study must be withdrawn from the study. The subject must be immediately discontinued from study medication and an Early Withdrawal Visit must be scheduled as soon as possible, but no later than the next scheduled visit. The subject should be encouraged to keep the SFU Visit as specified by the protocol.

Treatment should be started immediately.

Note that subjects with history of NTMB or active NTMB infection are excluded from the study regardless of prior or current therapy for this condition.

#### **12.6.1.1 Tuberculosis assessment by IGRA**

During conduct of the study, the TB assessment by IGRA (QuantiFERON TB GOLD is recommended) will be performed at Screening and should be repeated at Week 36/Early

Withdrawal Visit for all subjects. The test results will be reported as positive, negative, or indeterminate. UCB also recommends that a TB specialist be consulted where TB (latent or active) is suspected or if there are doubts regarding test results. If latent or active TB is identified, subject must undergo appropriate study-specified withdrawal procedures. The retest during Screening must be done during the protocol-defined Screening window (up to 4 weeks).

#### **12.6.1.2 Chest x-ray for tuberculosis**

A plain posteroanterior chest x-ray must be performed in the Screening Period unless one has been performed within 3 months prior to the Screening Visit. The chest x-ray (or, if done, Computed Axial Tomography [CAT] of the Chest) must be clear of signs of TB infection (previous or current) before first study medication administration. All chest imaging (particularly x-rays) should be available for review by the Investigator before randomization of the subject. The chest x-ray should be repeated only if the TB test was confirmed positive or any further evidence is suggestive of potential lung TB infection (eg, exposure). Radiographic findings suggestive of inactive TB or active TB may include but are not limited to: apical fibrosis, pleural thickening, pulmonary nodules, fibrotic scars, calcified granulomas, upper lobe infiltrates, cavitations and pleural effusions, calcified lung nodules, calcified hilar lymph nodes, and pericardial calcification.

The chest imaging must be negative for any old or recent TB infection as determined by a qualified radiologist and/or pulmonary physician. Any new clinically significant findings post Baseline on chest x-ray must be documented in the source documents and the eCRF as an AE.

#### **12.6.1.3 Tuberculosis questionnaire**

The questionnaire “Evaluation of signs and symptoms of tuberculosis” should be used as a source document. The questionnaire will assist with the identification of subjects who may require therapy for TB. A subject who answers “Yes” to the question “Has the subject been in close contact with an individual with active TB, or an individual who has recently been treated for TB?” at Screening is excluded. A “Yes” response to any of the other questions within the questionnaire at Screening should trigger further careful assessment to determine if subject has LTB or active TB (see Exclusion Criterion 13, [Section 6.2](#)). A “Yes” response to any of the questions during the study should trigger further assessments to determine if the subject has either LTB or active TB infection.

Subjects with a latent or active TB infection must be withdrawn from the study.

#### **12.6.1.4 Tuberculosis management**

##### LTB infection and active TB identified during study

During the study, subjects who develop evidence of LTB infection or active TB must immediately stop further administration of study medication and will be referred to an appropriate TB specialist (pulmonologist or infectious disease specialist) for further evaluation. Evidence of LTB infection is defined as subject’s IGRA test converts to positive or indeterminate (and confirmed indeterminate on repeat), or the subject’s questionnaire or history and physical indicates that TB infection or exposure may have occurred. Evidence of active TB includes, in addition to the aforementioned tests, signs and symptoms of organ involvement. In either situation, the subject should be carefully assessed by a TB specialist for active TB.

Subjects diagnosed with active TB or LTB infection should be withdrawn from the study and receive appropriate TB or prophylaxis therapy.

Any presumptive diagnosis or diagnosis of a TB infection is a reportable event. Confirmed active TB must be reported as an SAE. The Investigator is to complete and submit the TB follow up form provided.

The subject should be transferred to the care of his/her physician and managed according to the best available standard of care. Subjects identified as having converted to active TB during the study must be withdrawn and scheduled to return for the Week 36/EWD Visit as soon as possible but no later than the next scheduled study visit and complete all Week 36/EWD Visit assessments.

The subject should be encouraged to complete a SFU Visit (20 weeks after the last dose of study medication).

If infection with NTMB is identified during the study, the same procedure as for active TB acquired during the study must be followed.

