### 2.2.1 Clinical

Three clinical studies of bimekizumab have been completed: UP0008 in 39 subjects with mild to moderate plaque psoriasis, RA0124 in 30 healthy volunteers, and PA0007 in 53 subjects with psoriatic arthritis. Two studies (RA0123 and UP0031) are ongoing in subjects with moderate to severe rheumatoid arthritis and in healthy subjects, respectively.

UP0008 was a Phase 1, single ascending dose study in adults with mild to moderate psoriasis affecting  $\leq 5\%$  BSA. In this blinded study, single doses of up to 640mg (approximately 8mg/kg in an 80kg adult) were evaluated without any safety concerns. A total of 26 subjects with psoriasis with less than 5% of body surface involvement were treated with a range of single iv doses from 8 to 640mg. There were no clinically relevant safety findings identified at any dose and all doses were well tolerated. The pre-specified exploratory assessment of disease activity showed clinically relevant and statistically significant improvements at the higher doses studied.

RA0124 was a Phase 1, open-label, parallel-group, single-dose study in healthy subjects. The primary objective of this study was to determine the absolute bioavailability of single sc doses of bimekizumab (80mg and 160mg). The secondary objectives were to evaluate the dose proportionality of bimekizumab 80mg and 160mg sc, and to evaluate the safety and tolerability of these sc doses and 160mg given by iv infusion. In RA0124, the absolute bioavailability was

similar for the 2 doses tested (0.656 and 0.631 for the bimekizumab 80mg and 160mg sc doses, respectively). The PK of bimekizumab was linear in the tested dose range and the median  $t_{1/2}$  following sc administration was similar to that following iv administration (27.81 days and 28.25 days for bimekizumab 160mg sc and 160mg iv, respectively).

Bimekizumab has also been investigated in a Phase 1b, proof of concept, randomized, placebo-controlled, multiple dose study (PA0007). The primary objective of PA0007 was to assess the safety and PK of multiple dose administration of iv bimekizumab in subjects with psoriatic arthritis. Four active doses and a placebo were tested. Drug was administered as a loading dose at Week 0, and 2 additional doses were administered at Week 3 and Week 6. In each treatment group, subjects received a total of 3 doses of bimekizumab, administered every 3 weeks as shown below:

- 80mg loading dose followed by 40mg at Weeks 3 and 6

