### **3 STUDY OBJECTIVES**

#### **3.1 Primary objective**

The primary objective of this study is to evaluate the time-course of PASI over a 28-week period following the administration of bimekizumab given at Baseline and Week 4 to subjects with moderate to severe chronic plaque psoriasis.

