### 6.3 Withdrawal criteria

Subjects are free to withdraw from the study at any time, without prejudice to their continued care.

Subjects should be withdrawn from the study and encouraged to come for the SFU visit (20 weeks after the last received dose) if any of the following events occur:

1. Subject withdraws his/her consent.
2. The Sponsor or a regulatory agency requests withdrawal of the subject.

Subjects should be withdrawn from all study treatment and will be asked to return for the SFU Visit (20 weeks after the last received dose) if any of the following events occur:

1. There is confirmation of a pregnancy during the study, as evidenced by a positive pregnancy test.
- 2a. Subject develops an illness that in the opinion of the Investigator would interfere with his/her continued participation if the risk of continuing participation outweighs the potential benefit.
- 3a. Subject develops erythrodermic, guttate, or pustular form of psoriasis.
4. Subject considered as having either a suspected new LTB infection or who develop active TB or nontuberculosis mycobacterium (NTMB) infection during the study (including but not limited to, conversion demonstrated by interferon-gamma release assay [IGRA] or other diagnostic means) must be immediately discontinued from study medication, an Early Withdrawal Visit must be scheduled as soon as possible, but not later than the next regular visit.

Confirmed active TB is a serious adverse event (SAE) and must be captured on an SAE Report Form and provided to the Sponsor in accordance with SAE reporting requirements. As with all SAEs, periodic follow-up reports should be completed as per protocol requirements until such time as the TB infection resolves.

Additional information on TB policies are provided in [Section 12.6.1](#).

5. Subject is noncompliant with the study procedures or medications in the opinion of the Investigator.
6. Subject uses prohibited concomitant medications, with the exception of topicals, as defined in this protocol ([Section 7.8.2](#)), that may present a risk to the safety of the subject in the opinion of the Investigator and/or the Medical Monitor.

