## **6.4 Study Stopping Rules**

During the study, planned dosing and procedures may be discontinued or suspended for all subjects in any part of the study and appropriate follow up procedures established. Where it is

possible to do so without threatening the safety of subjects, such discontinuation/suspension should be discussed with the UCB Study Physician prior to its implementation.

Possible reasons for discontinuation or suspension of the study include (but are not limited to):

- A pattern of AEs occurs that contraindicates the further dosing of enrolled/additional subjects, including (but not limited to):
  - More than 1 subject meets any individual Withdrawal Criteria 4, 8a, 9a, 10 or 11 (as provided in [Section 6.3](#)), regardless of whether they met the same or different criteria.
  - Once a second subject meets any of those criteria, referral to the DMC may not be delayed while awaiting the outcome of either case.

If the above criteria are reached, the DMC will meet as soon as possible to determine whether discontinuation or suspension of the study should occur, and to determine what investigations, analyses, procedural amendments, or other actions should occur, before making any recommendation regarding the possibility of recommencing the study. Further details on the role of the DMC are provided in [Section 12.1.11](#) and [Section 12.7.4](#).

- If the Sponsor or its designees judges it necessary for medical, safety, regulatory, or any other reasons consistent with applicable laws, regulations, and GCP.

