## 8 STUDY PROCEDURES BY VISIT

Table 5–1 (schedule of study assessments) provides a general overview of study assessments. A list of procedures to be completed at each visit is described below.

- Visit windows of  $\pm 3$  days on either side of the scheduled dosing are permitted; however, the Investigator should try to keep the subjects on the original dosing schedule. The window of  $\pm 3$  days is relative to Baseline and applicable for all subsequent visits. Changes to the dosing schedule outside of the 3-day window must be discussed with the Medical Monitor.
- For the Safety Follow-Up Visit (20 weeks after the last dose), the visit should occur no more than 3 days prior to the scheduled visit date and within 7 days after the scheduled visit date (-3 days/+7 days).

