#### **12.6.2 Pregnancy testing**

Pregnancy testing will consist of serum testing at the Screening and SFU Visits. The pregnancy test will be urine at all other visits. If the subject is entering the extension study, a urine pregnancy test will be performed at SFU.

The Screening Visit serum pregnancy testing results must be negative and received and reviewed prior to randomization. A negative urine pregnancy test result should be obtained immediately prior to each administration of study drug and at all subsequent post-dosing visits. Pregnancy tests should be administered to all female subjects of childbearing potential, regardless of their use of birth control.

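### No scheduled TB contact question precedes the Week 4 or Week 16 dose, although Section 12.6.1.4 makes questionnaire-indicated exposure a reason to stop study medication

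*Protocol*

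**What the plan says.** Three parts of the protocol say what follows from possible TB exposure during the study, and they differ in strength.

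- Section 12.6.1.4 requires an immediate stop and referral to a TB specialist on evidence of latent infection. That evidence includes the case where the subject's "questionnaire or history and physical indicates that TB infection or exposure may have occurred". Symptoms are not required, and no step for resuming treatment is given.
- Section 12.6.1.3, which describes the questionnaire and its close-contact question, says that a Yes "response to any of the questions during the study should trigger further assessments".
- Section 6.3, criterion 4, covers a "Subject considered as having either a suspected new LTB infection or who develop active TB" or nontuberculous mycobacterial infection. It does not name exposure, but the word suspected is broad, IGRA conversion is only an example, and the reader is sent to Section 12.6.1.

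Doses are given at Baseline, Week 4 and Week 16. Section 8 lists the TB questionnaire at Screening, Baseline, Week 20 and Week 36/Early Withdrawal. The predose lists for Week 4 (Section 8.4) and Week 16 (Section 8.7) do not include it.

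**The concern.** A rule that stops dosing when a questionnaire shows exposure can work only if the questionnaire is answered before a dose. After Baseline, none of the answers scheduled in this study comes before a PS0016 dose. A subject who has had close contact with a TB case, feels well and does not mention it would receive the next injection without being asked. The doses at stake are the Week 4 dose in both arms and the Week 16 dose in Arm B (it is placebo in Arm A). An injected dose cannot be taken back. This concerns subject safety and the working of the protocol's own rule; it does not concern the efficacy analysis.

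**Working it through.** The plan gives no figure to reproduce. The check sets the schedule against the rule and counts days.

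**Inputs.** With Baseline as Day 0, doses fall on Days 0, 28 and 112 (Section 7.2). Visit windows are 3 days either side, relative to Baseline (Section 8). About 30 subjects are planned for Arm A and 15 for Arm B (Section 5.1.3). Visit content is taken from Sections 8.1 to 8.11, because the column positions in Table 5-1 are blurred in the text copy.

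| Visit | TB questionnaire | IGRA | Physical examination | PS0016 dose |
|---|---|---|---|---|
| Screening | yes | yes | yes | no |
| Baseline | yes | no | no | yes |
| Week 2 | no | no | no | no |
| Week 4 | no | no | no | yes |
| Weeks 8, 12 | no | no | no | no |
| Week 16 | no | no | no | yes |
| Week 20 | yes | no | no | no |
| Weeks 24, 28 | no | no | no | no |
| Week 36/EWD/SFU | yes | yes | yes | no |

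Medical history is scheduled only at Screening and Baseline (Table 5-1). The prompt at every visit (Section 12.1.4) asks about changes in health, not about contacts. The unscheduled-visit list (Section 8.13) has no TB questionnaire.

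**Time since the last questionnaire at each later dose.**
- Week 4: 28 - 0 = 28 days; window 25 to 31.
- Week 16: 112 - 0 = 112 days; window 109 to 115.

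**Time from the last dose to the next questionnaire.** 140 - 112 = 28 days; shortest 137 - 115 = 22; longest 143 - 109 = 34.

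**Active doses given without a same-day contact question.** Week 4: 30 + 15 = 45. Week 16: 15. A same-day question precedes the dose at 1 of 3 dosing visits now, and would do so at 3 of 3 with the fix.

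**Room for a delayed dose under the 24-day minimum interval (Section 7.2), at nominal visit days.**
- Week 4 dose delayed by h days: the gap to Week 16 is 84 - h, so 84 - h ≥ 24 gives h ≤ 60.
- Week 16 dose delayed by h days: the gap to a first extension dose at Week 20 is 28 - h, so 28 - h ≥ 24 gives h ≤ 4, if the minimum is read as covering the first extension dose.

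**Cost of the fix.** 2 x 45 = 90 questionnaires. Section 6.5 allows up to 10 replacements, so the number could approach 2 x 55 = 110. One missed Week 4 dose affects 1/45 = 2.2% of all subjects, or 1/30 = 3.3% of Arm A.

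**The case against.** The case for leaving the schedule alone has real content.

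- **Few events are likely.** Latent TB and known contact within 3 months before Screening are exclusions, and the questionnaire is repeated at Baseline. This stands, and it sets the severity.
- **Other routes exist.** A subject may volunteer a contact, symptoms would surface through the adverse event prompt, and Section 12.6.1 tells investigators to weigh social history. This also stands. What remains is symptom-free contact that nobody asks about.
- **Week 20 has a purpose.** Extension dosing can start at Week 20, 24 or 28, and the SFU assessments, which include the questionnaire and IGRA, must come before entry. The Week 20 questionnaire is therefore not simply late: it can protect the first extension dose. It cannot protect a PS0016 dose.

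Some stronger readings are tempting, and the documents do not support them.

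- **That every Yes must end treatment.** Section 12.6.1.4 points that way, but Section 12.6.1.3 asks for assessment. What is certainly missed is the prompt to act; whether it would be an automatic stop is unsettled.
- **That the protocol requires a check of every stop criterion before each dose.** For pregnancy it does: "A negative urine pregnancy test result should be obtained immediately prior to each administration of study drug". But Section 6.1 singles out the pregnancy test as the only Baseline laboratory result that must be known before dosing. The comparison shows that a predose check is feasible; it does not show a general rule.
- **That one visit matters more.** Weighting by time since the last questionnaire gives 45 x 28 = 1,260 subject-days for Week 4 and 15 x 112 = 1,680 for Week 16. This counts Arm B's first 28 days twice. Counted once, the split is 1,260 and 15 x 84 = 1,260. With no contact rate in the documents, neither version measures risk.
- **That withholding a dose lowers TB risk by a known amount.** The reported median half-lives, "27.81 days and 28.25 days for bimekizumab 160mg sc and 160mg iv, respectively", come from single doses in healthy subjects, and the documents give no relation between bimekizumab exposure and TB risk.

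**Conclusion.** The gap is real and narrow. For a subject on schedule, no questionnaire answer after Baseline can stop a PS0016 dose. The gap lasts 28 days (25 to 31) before the Week 4 dose and 112 days (109 to 115) before the Week 16 dose. It covers only symptom-free contact that the subject does not mention. The number of affected doses cannot be estimated from the documents and is expected to be small. A reader might infer bias in the Week 28 PASI result, but the questionnaire does not enter that analysis, which is descriptive (SAP Section 8.1.2). The conclusion assumes that sites follow the Section 8 lists and do not ask about contacts on their own initiative. It is a low-severity safety improvement, worth making because it is cheap.

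**What to change.** Add the existing TB questionnaire to the predose lists at Weeks 4 and 16 for all subjects (Table 5-1, Sections 8.4 and 8.7). Asking both arms preserves the blind. Keep the Week 20 and Week 36/EWD questionnaires, and leave the IGRA schedule unchanged.

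State that a Yes at a dosing visit means that day's dose is not given, and that the subject is assessed and referred under Sections 12.6.1.3 and 12.6.1.4 as they stand. Do not add a resumption rule by implication. If the sponsor wants dosing to resume once TB is ruled out, this should be written openly as a change to Section 12.6.1.4, with Medical Monitor agreement and the 24-day minimum interval kept. Section 8 already says: "Changes to the dosing schedule outside of the 3-day window must be discussed with the Medical Monitor". At Week 16 the minimum leaves little slack if an extension dose could follow at Week 20.

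The cost is about 90 short questionnaires at existing visits, more if subjects are replaced, with no new visit or routine test. The downside is an occasional delayed or missed dose. A missed Week 4 dose removes some data for the primary objective, the "time-course of PASI over a 28-week period following the administration of bimekizumab given at Baseline and Week 4", and for the PKPD model. Subjects then judged to have suspected latent TB would also count toward the Section 6.4 trigger for DMC review: "More than 1 subject meets any individual Withdrawal Criteria 4, 8a, 9a, 10 or 11".
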